#### **8.4.2 Method of Detecting AEs and SAEs**

The method of recording, evaluating, and assessing causality of AE and SAE and the procedures for completing and transmitting SAE reports are provided in [Appendix 2](#).

Care will be taken not to introduce bias when detecting AEs and/or SAEs. Open-ended and non-leading verbal questioning of the patient is the preferred method to inquire about AE occurrences.

#### 8.4.3 Follow-up of AEs and SAEs

After the initial AE/SAE report, the investigator is required to proactively follow each patient at subsequent visits/contacts. All SAEs, will be followed until resolution, stabilization, the event is otherwise explained, or the patient is lost to follow-up (as defined in Section 7.3). Further information on follow-up procedures is given in [Appendix 2](#).

#### 8.4.4 Regulatory Reporting Requirements for SAEs

Prompt notification by the investigator to the sponsor or designee of a SAE is essential so that legal obligations and ethical responsibilities towards the safety of patients and the safety of a study treatment under clinical investigation are met.

The sponsor has a legal responsibility to notify both the local regulatory authority and other regulatory agencies about the safety of a study treatment under clinical investigation. The sponsor will comply with country-specific regulatory requirements relating to safety reporting to the regulatory authority, Institutional Review Boards (IRB)/Independent Ethics Committees (IEC), and investigators.

Safety reports must be prepared for suspected unexpected serious adverse reactions (SUSAR) according to local regulatory requirements and sponsor policy and forwarded to investigators as necessary.

An investigator who receives a safety report describing a SAE or other specific safety information (eg, summary or listing of SAEs) from the sponsor will review and then file it along with the Investigator's Brochure and will notify the IRB/IEC, if appropriate according to local requirements.

Details of all pregnancies in female patients and female partners of male patients will be collected after the start of study treatment and until the Day 100 EOT visit.

If a pregnancy is reported, the investigator should inform the Sponsor within 24 hours of learning of the pregnancy and should follow the procedures outlined in [Appendix 3](#).

Abnormal pregnancy outcomes (eg, spontaneous abortion, fetal death, stillbirth, congenital anomalies, ectopic pregnancy) are considered SAEs.

#### 8.4.5 Disease-Related Events and/or Disease-Related Outcomes Not Qualifying as AEs or SAEs

Disease progression is an expected event in patients with advanced cancer. Therefore, disease progression itself diagnosed clinically or based on laboratory/testing should not be considered as an AE.

Since disease progression is an efficacy endpoint of this study it should be recorded separately in the appropriate eCRFs intended to capture tumor response assessment.

## 8.5 Treatment of Overdose

There are no clinical data with FPT155. In the event of a medical emergency due to suspected FPT155 overdose the Sponsor should be contacted as soon as possible. Monitoring and reporting a suspected treatment overdose should follow guidelines for AEs and SAEs. No specific antidote is available for treating overdose with FPT155. Management of any AEs due to overdose should be managed per Institutional practice.

## 8.6 Tumor Tissue

Tumor tissue should be collected in accordance with the Schedule of Assessments ([Table 1](#), [Table 2](#), [Table 3](#), and [Table 4](#)) and Section 4.1.4.

### 8.6.1 Archival Tumor Tissue

Archival tumor tissue from an excisional, incisional or core needle biopsy, as fine needle aspirates or other cytology specimens are insufficient for downstream biomarker analyses. Patients must consent to undergo a fresh tumor biopsy during screening if archival tumor tissue is not available. Archival tissue will be collected as follows:

### 8.6.2 Tumor Tissue Biopsy

The following guidelines apply to patients who consent for tumor biopsy:

- All patients that consent to a pre-treatment biopsy must have at least one tumor site that can be biopsied and be willing to have pre-treatment and on-treatment biopsies, from the same lesion where feasible.
- Biopsies will be performed according to the treating institution's own guidelines. These biopsies must be excisional, incisional or core needle biopsies, as fine needle aspirates or other cytology specimens are insufficient for downstream biomarker analyses.
- If a pre-treatment biopsy has been performed as part of the patient's standard of care within 28 days prior Cycle 1 Day 1, if the sample is available to study Sponsor and has sufficient evaluable tumor content, the pre-treatment biopsy does not need to be repeated.
- Sites for biopsy must be distinct from target lesions used for efficacy assessment
- Patient must have recovered from any acute adverse effects of the biopsy procedure prior to dosing

Patients may also have an (optional) biopsy upon documented disease progression. If available, tumor tissue obtained from post-treatment procedures such as surgery may also be collected.

## 8.7 Pharmacokinetics

PK parameters are evaluated in this study in accordance with the Schedule of Assessments ([Table 3](#) and [Table 4](#)).

Serum samples will be collected for measurement of concentrations of FPT155 and pembrolizumab as specified in the Schedule of Assessments. Instructions for the collection and handling of biological samples are in the laboratory manual. The actual date and time (24-hour clock time) of each sample will be recorded. The measurement of serum FPT155 and pembrolizumab concentration will be performed using validated ELISAs.

## 8.8 Pharmacodynamics

Pharmacodynamic parameters will be evaluated in this study in accordance with the Schedule of Assessments ([Table 3](#) and [Table 4](#)).

Venous blood samples will be collected for measurement of immune phenotype changes due to study intervention by (including but not limited to) flowcytometry or cytokine or ribonucleic acid (RNA) analysis. Specific time points are listed in the Schedule of Assessments.

Tumor biopsy samples at screening and prior to Cycle 3 Day 1 will be collected from select patients for measurement of immune phenotype changes due to study intervention by (including but not limited to) immune histochemistry or RNA analysis. Specific time points are listed in the Schedule of Assessments.

## 8.9 Biomarkers

Samples for predictive and pharmacodynamic biomarker assessment will be collected and processed according to instructions provided in a separate laboratory manual. Additional guidance for sampling and procedures is provided in the following sections:

- Specific timing requirements for study assessments and procedures are outlined in the Schedule of Assessments.
- Guidance for the specific timing and sample collection of PK, immunogenicity, and pharmacodynamic sample collection: [Table 3](#) and [Table 4](#) Schedule of Pharmacokinetic, Immunogenicity, and Pharmacodynamic Blood Sample Collection.

A variety of endpoints that could monitor drug activity or potentially predict clinical response to study intervention may be investigated in peripheral blood and archival and/or fresh tumor specimens, collected from patients prior to and during treatment. Data from these analyses will be evaluated for association with response and/or safety data.

Samples will be stored in a secure storage space with adequate measures to protect confidentiality.

### **8.9.1      Immunogenicity Assessments**

Antibodies to FPT155 and pembrolizumab will be evaluated in serum samples collected from all patients according to the Schedule of Assessments.

Serum samples will be screened for antibodies binding to FPT155 and pembrolizumab and the titer of confirmed positive samples will be reported. Other analyses may be performed to further characterize ADAs to FPT155 and pembrolizumab.

The detection and characterization of antibodies to FPT155 will be performed using a validated ligand binding assay. Samples collected for detection of antibodies to FPT155 will also be evaluated with concurrent FPT155 serum concentration samples to enable interpretation of the effect of the antibody on serum concentration and other pharmacokinetic parameters. Antibodies may be further characterized and/or evaluated for their ability to neutralize the activity of FPT155. Samples may be stored until the Clinical Study Report (CSR) is written and approved or up to the stability date established during assay validation (typically this will be the stability period established for serum drug concentration samples) to enable further analysis of immune responses to FPT155 if needed.

### **8.9.2      RNA Expression Research**

Transcriptome studies may be conducted using RNA sequencing or alternative equivalent technologies, which facilitates the simultaneous measurement of the relative abundances of thousands of RNA species resulting in a transcriptome profile for each blood and tumor sample. Alternatively, targeted RNA expression analysis may be performed using targeted RNA sequencing assays and/or alternative equivalent technologies. This will enable the evaluation of baseline correlates, or changes in transcriptome profiles that may correlate with biological response relating to study intervention.

The samples may also be used to confirm findings by application of alternative technologies.

### **8.9.3      Immunohistochemistry/Immunofluorescence**

Immunohistochemistry (IHC) or immunofluorescence (IF) studies may be conducted using archival tumor and fresh biopsy samples. This will enable the evaluation of baseline correlates, or changes in tumor immune profiles that may correlate with biological response relating to study intervention.

The samples may also be used to confirm findings by application of alternative technologies.

#### **8.9.4 PBMC Collection**

PBMCs will be isolated from peripheral blood samples at various time points. Flow cytometry and/or alternative equivalent technologies may be performed to understand baseline correlates of immune phenotype, and/or changes in immune phenotype due to study intervention.

The samples may also be used to confirm findings by application of alternative technologies.

#### **8.9.5 Cytokine Analysis**

Cytokine analysis by ELISA based and/or alternative equivalent technologies may be performed to understand baseline correlates, and/or changes in cytokine profile due to study intervention.

The samples may also be used to confirm findings by application of alternative technologies.

#### **8.9.6 Circulating Tumor DNA Blood Assay**

Circulating tumor DNA-containing plasma will be isolated from peripheral blood samples at various time points. Targeted deoxyribonucleic acid (DNA) sequencing and/or alternative equivalent technologies may be performed to identify tumor driver mutations and/or estimate tumor mutation burden and understand their association with biological response relating to study intervention.

The samples may also be used to confirm findings by application of alternative technologies.

### **8.10 Medical Resource Utilization and Health Economics**

Medical resource utilization and health economics parameters are not evaluated in this study.

## 9.0 STATISTICAL CONSIDERATIONS

All analyses will be descriptive and will be presented by phase, dose group, cohort and overall as appropriate. In addition, all patients dosed at the MTD and/or RD will also be summarized as appropriate. Data collected in this study will be presented using summary tables and patient data listings. Continuous variables will be summarized using descriptive statistics, specifically the number of subjects, mean, median, standard deviation (SD), minimum, and maximum. Categorical variables will be summarized by frequencies and percentages.

A change to the data analysis methods described in the protocol will require a protocol amendment only if it alters a principal feature of the protocol. The statistical analysis plan (SAP) will be finalized prior to database lock. Any changes to the methods described in the final SAP will be described and justified in the clinical study report.

### 9.1 Statistical Hypotheses

Not applicable.

### 9.2 Sample Size Determination

This study is designed as a dose escalation, dose exploration, and dose expansion study with objectives that include determination of an MTD and/or RD and assessments of the safety and tolerability of FPT155 as monotherapy and in combination with pembrolizumab. The sample size of this study was not determined by strict statistical considerations. The total number of patients planned for this study is estimated to be approximately 408.

The sample size of Phase 1a is defined by the requirements of the accelerated titration and 3+3 dose escalation design. Approximately up to 108 patients will participate in Phase 1a monotherapy, depending on the number of dose levels evaluated and the incidence of DLTs; this includes up to 58 patients in the Phase 1a monotherapy dose escalation portion and allows for up to approximately 50 patients in the Phase 1a monotherapy dose exploration to further explore safety, PK, PD, and clinical activity at one or more dose levels (conditional upon the dose level clearing dose escalation criteria). Approximately up to 60 patients will participate in Phase 1a combination, depending on the number of dose levels evaluated and the incidence of DLTs; this includes up to 30 patients in the Phase 1a combination dose escalation, and up to 30 patients in the Phase 1a combination dose exploration.

For the objective of estimating the ORR of FPT155 in Phase 1b monotherapy, it is estimated that up to 30 patients will be enrolled to ensure 25 evaluable patients in each cohort. [Table 10](#) displays the corresponding 2-sided 90% confidence interval (CI) and the precision for the various observed response rates ([Agresti 1998](#)) based on 25 evaluable patients. The sample size of 25 is chosen to ensure that it will allow to exclude 10% when the observed ORR is 24% or higher in each cohort.

Approximately 240 patients will participate in Phase 1b monotherapy. Phase 1b monotherapy will consist of up to 8 cohorts of approximately 30 patients each.

**Table 10: Two-Sided 90% Confidence Intervals of the Observed Response Rates**

Sample Size	Observed Response Rate	90% CI	Precision (longest one-sided CI length*)
25	5/25 (20%)	(8%, 38%)	18%
	6/25 (24%)	(11%, 42%)	18%
	7/25 (28%)	(14%, 46%)	18%
	8/25 (32%)	(17%, 50%)	18%
	9/25 (36%)	(20%, 54%)	18%
	10/25 (40%)	(24%, 58%)	18%

Abbreviations: CI = confidence interval.

\*Distance from the observed response rate to the lower or upper CI boundary.

### 9.3 Populations for Analyses

The following analysis populations are defined for the study as follows:

Population	Description
Enrolled	All patients who sign informed consent and are registered as enrolled in IVRS/IWRS.
Efficacy Population	All patients who have received any portion of at least one dose of study drug.
DLT-Evaluable Population	All patients enrolled into Phase 1a dose escalation portion of the study who received at least 1 dose of all assigned study drug(s) and remain on study for the 21-day DLT evaluation, or who experienced a DLT before clearing the 21-day DLT evaluation interval.
Safety Population	All patients who have received any portion of at least one dose of any study drug.
Response-Evaluable Population	All patients who met eligibility criteria, received at least one dose of any study drug, have measurable tumor lesions at baseline, and have at least one post-baseline disease assessment unless the death and clinical progressive disease occurred prior to the first post baseline disease assessment.
PK-Evaluable Population	All patients who have received at least one dose of study drug and have had sufficient PK sample for the calculation of at least one PK parameter on at least one Study Day.

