#### 9.4.1 Efficacy Analyses

The primary efficacy analyses (Table 11) will be performed on the efficacy population. Efficacy analyses based on the response-evaluable population may be performed as a sensitivity analysis. Details of the censoring scheme on time-to-event endpoints such as DOR and PFS will be described in the SAP.

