4.5 Response-Evaluable Population

All patients who met eligibility criteria, received at least one dose of any study drug, have measurable tumor lesions at baseline, and have at least one post-baseline disease assessment unless the death and clinical progressive disease occurred prior to the first post baseline disease assessment.

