6.2 Efficacy Analyses

Tumor response assessment will be performed by the investigator per RECIST v1.1 guidelines. The tumor response will be classified to: complete response [CR], partial response [PR], stable disease [SD], or progressive disease [PD].

The Efficacy analyses listed in the [Table 9](#) will be performed on the efficacy population as primary analysis, and on the response-evaluable population as a sensitivity analysis. Efficacy analysis will be performed separately for Phase 1a Monotherapy Dose Escalation/Exploration, Phase 1b Monotherapy Dose Expansion and Phase 1a Combination Dose Escalation/Exploration.

Table 9 Efficacy analysis

Phase	Efficacy Endpoint	Efficacy Analysis
Phase 1a Monotherapy Dose Escalation/Exploration	Exploratory	[REDACTED]
Phase 1b Monotherapy Dose Expansion	Secondary	ORR, DOR, PFS, DCR
	Exploratory	[REDACTED]
Phase 1a Combination Dose Escalation/Exploration	Secondary	ORR
	Exploratory	[REDACTED]

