6.2.1 Efficacy Endpoint: ORR

Objective Response Rate (ORR) is defined as the total number of patients with confirmed responses of either complete response (CR) or partial response (PR), as determined by the investigator per RECIST v1.1, divided by the total number of patients who are evaluable for a response. The best overall response (BOR) is the best response documented from first dose until the end of study, first disease progression, death, or start of new anti-cancer therapy, whichever is earlier. Subjects, who do not have sufficient baseline or on-study tumor status information to be adequately assessed for response status (i.e., those with BOR of not evaluable [NE]), or received anticancer therapy other than the study treatment, will be considered as non-responders and will be included in the denominators in calculations of response rates.

For the confirmed BOR, the algorithm below should be followed. The hierarchy of the categories for confirmed BOR is in the order listed.

- Confirmed CR: Check if the longest consecutive duration of CR (allow NE in between; duration starts at CR and ends at CR) is ≥ 4 weeks, if yes, set BOR to CR; otherwise:
- Confirmed PR: Check if the longest consecutive duration of PR (allow NE or CR in between; duration starts at PR and ends at PR/CR) is ≥ 4 weeks, if yes, set BOR to PR; otherwise:
- SD: Check if the best time-point response is CR or PR or SD, if yes, set BOR to SD; otherwise:

- PD: Check if the best time-point response is PD, set confirmed BOR to PD.
- NE: Otherwise set to NE.

Estimate of ORR and corresponding 2-sided exact 90% CI using the Clopper-Pearson method will be provided by treatment and overall. The Clopper-Pearson exact 90% CIs will be from SAS FREQ procedures with option BINOMIAL (EXACT). Patients who don't have any postbaseline adequate tumor assessments will be counted as non-responders.

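### Read literally, the response-evaluable population drops patients with only one of early death or clinical progression, which biases its sensitivity analysis upward

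*Protocol*

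**What the plan says.** Protocol 9.3 admits a patient to the Response-Evaluable Population if he or she was eligible, was dosed, had measurable disease at baseline and had at least one post-baseline assessment. The last condition is waived in one case only: "unless the death and clinical progressive disease occurred prior to the first post baseline disease assessment". SAP 4.5 carries the same clause: "have at least one post-baseline disease assessment unless the death and clinical progressive disease occurred prior to the first post baseline disease" assessment.

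The set has a defined but secondary role. Protocol 9.4.1 says the primary efficacy analyses "will be performed on the efficacy population. Efficacy analyses based on the response-evaluable population may be performed as a sensitivity analysis". SAP 6.2 is firmer and says the efficacy analyses "will be performed on the efficacy population as primary analysis, and on the response-evaluable population as a sensitivity analysis". The Efficacy Population in Protocol 9.3 has no scan requirement: "All patients who have received any portion of at least one dose of study drug".

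For ORR, SAP 6.2.1 adds that patients without enough tumour information "will be considered as non-responders and will be included in the denominators in calculations of response rates". It repeats the rule for those with no adequate post-baseline assessment. The section nevertheless opens by defining ORR as responders "divided by the total number of patients who are evaluable for a response". SAP 6.2.2 uses the same denominator phrase for DCR and has no rule of its own for unassessed patients.

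On sample size, Protocol 9.2 expects that "up to 30 patients will be enrolled to ensure 25 evaluable patients in each cohort".

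**The concern.** A waiver of this kind exists to stop early treatment failures from leaving the denominator because they failed before they could be scanned. With the two events joined by *and*, the literal clause keeps only patients who had both. Two groups are lost:

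- patients who die before the first scan with no recorded clinical progression, for example from toxicity or an unrelated cause;
- patients who progress clinically before the first scan, are alive, and are never scanned.

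The first scan is due six weeks after the first dose (Protocol 8.1.1), so in advanced solid tumours there is room for such cases. None of these patients can be a responder or have documented disease control. Removing them can therefore only raise the two rates. What is at stake is the sensitivity analysis: it would look better than the primary result for a reason unrelated to drug activity, and could be read as supportive.

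**Working it through.** **Inputs**

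- Cohort size: up to 30 enrolled, 25 evaluable (Protocol 9.2). I take all 30 as treated.
- Interval: two-sided exact 90%, Clopper-Pearson (Protocol Table 11, SAP 6.2.1).
- k, the number of unscanned patients with exactly one of the two events: not in the documents. Assumed 0 to 5, the upper end being the plan's own allowance, 30 − 25 = 5 (16.7% of 30).
- Responders: 6, chosen because 6/25 is the plan's benchmark row.
- No exclusions other than these k patients.

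**Formula.** For x responders in n, with B the beta quantile: lower limit = B(0.05; x, n − x + 1); upper limit = B(0.95; x + 1, n − x).

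**The plan's own figure.** For 6/25, lower = B(0.05; 6, 20) = 11.0% and upper = B(0.95; 7, 19) = 42.0%. Protocol Table 10 and SAP Table 4 give (11%, 42%). The other rows also agree after rounding: 5/25 8.2–37.5; 7/25 13.9–46.2; 8/25 17.0–50.4; 9/25 20.2–54.4; 10/25 23.6–58.3.

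**Response-evaluable ORR under the literal clause.** The denominator is 30 − k.

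| k | x/n | ORR | 90% CI | Lower limit above 10%? |
|---|---|---|---|---|
| 0 | 6/30 | 20.0% | 9.1–35.7 | no |
| 1 | 6/29 | 20.7% | 9.4–36.8 | no |
| 2 | 6/28 | 21.4% | 9.8–38.0 | no |
| 3 | 6/27 | 22.2% | 10.1–39.2 | yes |
| 4 | 6/26 | 23.1% | 10.6–40.5 | yes |
| 5 | 6/25 | 24.0% | 11.0–42.0 | yes |

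The relative inflation is 30/(30 − k): 3% at k = 1, 11% at k = 3, 20% at k = 5.

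**How narrow the crossing is.** With 7 responders the lower limit is above 10% even at k = 0 (7/30: 11.5%). With 5 it is below 10% even at k = 5 (5/25: 8.2%). Within this range only exactly 6 responders with k of 3 or more changes sides.

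**Chance of crossing if the true ORR is 10% in all 30 treated.** Take k as fixed, with all k patients among the non-responders. For k = 0 to 2, 7 responders are needed: P(X ≥ 7) = 0.026. For k = 3 to 5, 6 are enough: P(X ≥ 6) = 0.073, with X binomial (30, 0.10).

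**DCR in the same set.** With an illustrative 15 patients controlled: 15/30 = 50.0% at k = 0, 15/27 = 55.6% at k = 3, 15/25 = 60.0% at k = 5.

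**Primary ORR.** On the Efficacy Population with the SAP 6.2.1 rule, the k patients stay in as non-responders. The result is 6/30 = 20.0% (9.1–35.7) whatever k is.

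**The case against.** The strongest objection concerns reach. A reader might infer that the trial's headline response rates are inflated. The documents do not support that. Protocol 9.4.1 and SAP 6.2 both place the primary analysis on all treated patients, and SAP 6.2.1 keeps unassessed patients in the ORR denominator. That stands in full.

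A reader might also reason that ORR, DCR and the 25-patient precision statement all speak of evaluable patients, so this set drives them too. None of those places uses the defined term Response-Evaluable Population, and SAP 6.2 assigns ORR and DCR to the Efficacy Population first. The denominator phrase does sit badly with an all-treated analysis, most visibly for DCR, which lacks a non-responder rule of its own. That is a separate ambiguity, and changing *and* to *or* would not settle it.

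Next, *and* may be a loose list of two separate exceptions. That is possible, and neither document rules it out. But the DLT-Evaluable definition in the same table uses *or* for alternatives, and the RECIST guideline in Protocol Appendix 6 (4.4.4) asks each protocol to describe early death and early progression clearly. A population definition has to be programmed as written.

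Finally, the size depends on an assumed k. Patients excluded for ineligibility, no measurable disease, or withdrawal or missed scans without either event stay excluded under either wording, so the edit would not generally turn 25 into 30. Nor does any decision turn on 10%: the trial has no hypothesis, no interim analysis, and safety as the Phase 1b primary endpoint. All of this stands and limits the weight of the point.

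**Conclusion.** The point holds for the response-evaluable sensitivity analysis only. Followed literally, the clause removes non-responders selectively, so the direction of bias is certain: upward for ORR and DCR in that set. The size is not known, because k is not given. For k = 0 to 5 of 30 and 6 responders, ORR moves from 20.0% to at most 24.0%, and the lower 90% limit passes 10% from k = 3 (6/27: 10.1%). This rests on the literal reading of *and*, on 30 treated patients, and on no other exclusions.

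It would be tempting to go further and say that the clause can manufacture the plan's benchmark of excluding 10%. In the sensitivity set, with exactly 6 responders and at least three such patients, the limit does cross. In the primary ORR it cannot, and the plan attaches no decision to that crossing. This is a definition to repair before the analysis is programmed. It does not call the primary ORR into question.

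**What to change.** In Protocol 9.3 and SAP 4.5, join the two events with *or* and drop the article before death, so that the waiver applies where death or clinical progressive disease came before the first post-baseline assessment. State in both places that patients kept by the waiver count as non-responders for ORR and as not having disease control for DCR in that set.

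This is one conjunction and one sentence in two documents, with no new data, visits or patients. The cost is a slightly lower response rate in the sensitivity analysis. The separate denominator ambiguity in SAP 6.2.1 and 6.2.2 could be cleared at the same time by naming the population for each rate, but that is an additional change.
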